**The Motor Control Consequences of Excessive Physical Therapist Support in
Individuals with Stroke (NCT04856527)**

University of Cincinnati IRB Protocol 2020-1072

Most recent IRB approval: 2021-10-07

STUDY PROTOCOL AND STATISTICAL ANALYSIS PLAN

Study Protocol

Participants

Twenty participants aged 21-85 years¹ previously diagnosed with stroke (>1-month prior to enrollment to ensure medical neurologic stability) will participate in Experiment 1 (10 participants in experimental group, 10 participants in control group). Participants will be randomly assigned to a group. Participants must demonstrate independence or modified independence during ambulation (defined as the ability to ambulate with no physical assistance and use an assistive device as needed). Participants must score 0-3 on the Modified Rankin Scale (de Haan et al., 1995; Rankin, 1957), which indicates complete independence to moderate disability but able to walk without assistance. Participants must be able to maintain standing balance for >2 minutes with no physical support and maintain grasp of a handheld object with at least one hand. Participants are permitted to be active in programs of physical therapy or occupational therapy at the time of enrollment. All gender identities and all races/ethnicities will be eligible for participation.

Participants with stroke will be excluded due to limited language/cognitive abilities, deafness, blindness, or serious motor impairment that outright prevents performance of the experimental tasks (e.g., severe upper or lower extremity spasticity). Participants will be excluded if they are pregnant. Participants will also be excluded if they experience pain with weightbearing >4/10. Participants will complete the Mini Mental State Exam (Folstein et al., 1975) prior to study start to ensure cognitive capacity to engage in and consent to the study. Participants will be excluded if they have any other medical condition that would preclude the valid administration of the study measures, specifically seizure disorders, additional neurologic conditions beyond stroke, or significant musculoskeletal conditions (e.g., lower limb amputation).

Participants with stroke will be recruited from a large outpatient neurologic rehabilitation clinic part of a larger, nonprofit medical center in the midwestern United States. Further, participants will also be recruited from the UC Stroke Recovery Registry. This registry contains over 750 persons with chronic stroke who have expressed a desire to be involved in stroke-related research at UC. The registry is shared among researchers in the College of Allied Health Sciences, the College of Medicine, and the College of Nursing. All participants will receive compensation for time and travel.

Materials and Apparatus

Participants will be placed in a virtual environment created with the Unity game engine (Unity Technologies, San Francisco, CA) while donning a VIVE virtual reality (VR) headset (HTC Corporation, Bellevue, WA). Postural sway will be measured using a force platform (AMTI AccuSway, Advanced Mechanical Technology, Watertown, MA). For the

¹ This is the age range *approved* by the IRB. Age range will be narrowed once it is ascertained what range is available for recruitment. Most likely, participants will be > 60 years. However, if a large sample of younger adults < 45 years is available, that will become an eligibility criterion, and the study will be conducted with young adults with stroke.

transfer task, light finger force production will be measured with a 1500 g force transducer (Measurement Specialties, Inc., Dayton, OH). A visual display created in Processing (v.3.5.4) will communicate level of light force production to participants. The virtual environment will be rendered at a rate of 90 Hz. Postural sway data and light force production will be sampled continuously at a rate of 150 Hz.

Experiment 1: Postural Support and Task Learning

Pre-Test

In Experiment 1, participants will be required to learn an upper limb precision aiming task while receiving postural support (i.e., balance facilitation) or no postural support. Baseline performance will be measured prior to a practice period. For this pre-test, participants will stand on the force platform for 30 s trials. Within the VR environment, participants will see an anteriorly placed circular target and will be instructed to maintain the position of a virtual laser pointer in the target via a handheld device in the dominant hand (or both the non-paretic and paretic hands for participants with stroke) with the upper limb held at the side. The target will change color to communicate task accuracy to participants: When the virtual laser is correctly positioned within the target, the target will be blue, but misaiming will turn the target red, indicating the need to correct the laser position. Participants will only visualize the laser and target in VR; there will not be a virtual representation of the upper limb. Participants with stroke will complete two 30 s pre-test trials with each hand (paretic and non-paretic). Postural sway and projection of the laser will be measured and recorded.

Transfer Task

As therapists expect that training in a set of tasks might benefit performance of other similar but untrained tasks (i.e., transfer), a task to assess transfer will also be implemented. This task will be completed both prior to the practice period (to obtain a baseline level of performance for comparison after practice) and after the practice period. In the transfer task, participants will attempt to use their dominant hand (or both non-paretic hand and paretic hand for participants with stroke) second digit to produce a specified level of light touch force (0.5-1 N to prevent physical stabilization) on the force transducer. Like the laser pointer task, this task requires integration of postural control with precision manual performance (e.g., Riley et al., 1999b). Participants will receive visual feedback regarding their level of light touch force production on a visual display. A vertical bar will appear on the screen. The bar will increase in vertical size with increased force production and decrease in size with less force production. The bar will change color to reflect the level of force production. When the bar is blue, the desired level of force production has been achieved. When the bar is red, the participant needs to alter the level of force production. A horizontal line will also indicate target force production. Participants will complete two 30 s trials of the transfer task. Participants with stroke will complete the transfer trials with each limb.

Practice

Following the pre-test and baseline transfer task, participants will engage in 10, 1 min practice blocks in which they are to practice the laser task with the target positioned

laterally. This lateral placement of the target during the practice period (as opposed to the anterior position of the pre-test) will prevent one group of participants from practicing under the exact conditions of the pre-test, which could bias the results. This will also allow for an assessment of differences in sway variability that may facilitate performance at post-test, thus providing insights about generalizability. The control group will receive no physical support to maintain balance. The experimental group will receive physical support (whether physical support is warranted or not) to minimize postural sway fluctuations. Participants with stroke will use the paretic hand. Participants will be outfitted with a gait belt, and physical support will be provided through the use of the gait belt and other traditional physical therapy guarding techniques (O'Sullivan et al., 2019). Thus, participants in this group will not be required to coordinate posture and task performance because postural stabilization will be provided externally through physical support. Postural sway and virtual laser position will be synchronously recorded during the practice period. Participants will rest for a self-selected period between each trial.

Immediate Post-Test and Retention

Participants will complete a post-test following the same procedure as the pre-test (i.e., target task). The post-test will also involve the previously described transfer task. Participants will complete two 30 s trials of each task (target/force production). Participants with stroke will complete the trials with each limb. Task and condition will be randomized. No physical support will be provided in the post-test.

Design

To evaluate the learning effect in participants with stroke, the two groups (experimental, control), two hands (paretic, non-paretic), and two test conditions (pre-test, immediate post-test) will result in a $2 \times 2 \times 2$ mixed design for Experiment 1. Participants with stroke will complete 2 trials of each test condition per limb for a total of 8 test trials per participant. To evaluate the role of therapist support during practice, each participant will complete 10 practice trials. Participants will complete 4 trials (2 trials per limb) of the transfer task before and after practice for a total of 8 trials.

Proposed Data Analysis

All data processing and analyses will be completed using custom R scripts (v.4.0.3). All postural sway data (i.e., center of pressure—COP) will be filtered through a 4th-order lowpass zero-lag Butterworth filter with a cut-off frequency of 6 Hz prior to analysis.

Recurrence Quantification Analysis (RQA)

RQA (Webber & Zbilut, 2005) will be used to assess the regularity of postural sway. RQA quantifies the patterning, non-stationarity, and complexity of biological time series through the analysis of local recurrences in a reconstructed phase space (Riley et al., 1999a). Recurrence plots (RPs) provide a visualization of patterns of recurrence, where a single point on the RP indicates a recurrence and a line indicates continuing recurrence (Coco & Dale, 2014). A variety of metrics are used to quantify these patterns. Percent determinism (%DET) is the percentage of recurrent points which fall on diagonal lines

and reflects how often the system repeats the same sequence of points. Thus, higher %DET is indicative of a system with more regularity. Maximum line length (MAXLINE) is the length of the longest diagonal line segment on the RP, indicating the maximum duration of time that the system is revisiting an area of reconstructed phase space. Mean line length (MEANLINE) is the average length of diagonal line segments on the RP, indicating the average duration of time that the system is revisiting an area of phase space. In the context of the current study, reduced task-sensitive adjustments (i.e., modulation in task relevant direction) in %DET, MAXLINE, and MEANLINE of postural sway (hypothesized to exist following constraining posture/task) would indicate a more regular postural control system—one that is prone to repeating the same behaviors. RQA metrics will be calculated separately for each plane.

Sample Entropy (SampEn)

SampEn (Richman, Lake, & Moorman, 2004) will be used to evaluate changes in the predictability of postural sway as a convergent measure to complement RQA. SampEn evaluates the predictability of the next state of a system, given what is known about the current state of a system (Yentes, 2016). SampEn has been widely used to assess the regularity of postural control across a variety of task conditions and populations (e.g., Schmit et al., 2016). SampEn will be calculated separately for each plane.

Traditional Analyses

Due to the wide use of COP path length and standard deviation (SD) of COP in the literature, these metrics will also be measured to further quantify changes in postural sway. These metrics are also important for assessing the distribution of sway in each plane as a function of task demand. COP path length refers to the amount of displacement of the location of the (resultant) vertical ground reaction force vector. Increased COP path length is often interpreted as reduced stability. SD of the COP is the typical method used to quantify the variability in COP trajectories. Higher values for SD of the COP indicate increased variability. COP path length is a bi-planar measure whereas SD of the COP will be calculated separately for each plane.

Supra-Postural Task Performance

Root mean square (RMS) deviation of the observed supra-postural task performance from the expected values will be used to determine the accuracy of supra-postural task performance. For Experiments 1 and 2, this will be defined as the deviation of the laser position from the target. For the transfer task, this will be defined as the deviation from the target range of light touch force production.

Statistical Analysis

To characterize learning of the practiced supra-postural laser/target task and the associated postural sway patterns, trials (error score and postural sway metrics) for both experiments will be submitted to mixed-effects models. Group (experimental, control), test condition (pre-test, immediate post-test), limb (paretic, non-paretic), and their interactions will be entered as fixed effects, and participant will be entered as a random effect. To assess performance (error score and postural sway metrics) during the practice period, trial number (1-10), group (experimental, control), and their interaction will be

entered as fixed effects and participant will be a random effect. For the transfer task (error score and postural sway metrics), group (experimental, control), test condition (pre-test, immediate post-test), limb (paretic, non-paretic), and their interactions will be entered as fixed effects, and participant will be entered as a random effect. A backward stepwise approach will be used for model building. Simple effects and pairwise comparisons will be used to follow up on significant interactions.

Relevant References

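### Must eligibility require a paretic arm, given that practice and the limb factor assume one?

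*Combined protocol and SAP*

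**What the plan says.** The combined protocol and SAP sets eligibility in the Participants section. It asks for a stroke diagnosis, walking without physical help, standing balance and the ability to "maintain grasp of a handheld object with at least one hand". It adds that "Participants must score 0-3 on the Modified Rankin Scale". No criterion asks for hemiparesis or arm paresis. The same section excludes people with "serious motor impairment that outright prevents performance of the experimental tasks" and gives severe spasticity of an upper or lower limb as an example.

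The procedures assume one paretic and one non-paretic hand:

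- **Pre-Test:** two laser trials with each hand, repeated at post-test.
- **Practice:** "Participants with stroke will use the paretic hand".
- **Design:** hand is one of the three two-level factors. For the transfer task, "Participants will complete 4 trials (2 trials per limb) of the transfer task before and after practice for a total of 8 trials".
- **Statistical Analysis:** for the learning and transfer models, "limb (paretic, non-paretic), and their interactions will be entered as fixed effects". The practice model has only trial number, group and their interaction.

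The sample is 20, with "10 participants in experimental group, 10 participants in control group".

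**The concern.** Two mismatches stand out between who may enter and what they must do.

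First, a person whose stroke left neither arm weak meets every listed criterion, and the same is true of someone with both arms affected. Neither has an obvious paretic hand, so the plan leaves open which hand practises and which level of the limb factor each trial receives. The dominant-hand wording in Pre-Test and Transfer Task is no fallback, because it is written as the alternative to the rule for participants with stroke. The motor exclusion does not help either, because it removes people with too much impairment, not those with none.

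Second, the inclusion rule accepts grasp with one hand, although both hands must hold the device. Someone able to grasp only with the non-paretic hand might be admitted and then give no practice data.

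At stake would be the meaning of the limb effect and its interactions, and some practice data, in a study with 10 per group.

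**Working it through.** **1. Trial count (Design, Transfer Task, Practice).**

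- Laser test: 2 hands × 2 trials × 2 test conditions = 8, as the Design section states.
- Transfer: 2 × 2 × 2 = 8, as stated.
- Practice: 10, as stated.
- Total: 8 + 8 + 10 = 26.
- Paretic hand: 4 laser + 4 transfer + 10 practice = 18, and 18/26 = 69%.
- Of these 18, the 4 transfer trials are finger presses, so 4 + 10 = 14 need the handheld device.

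**2. How many people.** The documents give no share of participants without arm paresis. They name two sources, an outpatient neurological rehabilitation clinic and a stroke registry, and describe neither by arm function. The Rankin range is explained only as running from full independence to moderate disability, which says nothing direct about the arm. As an assumption, take k = 1 to 4 of 20. Then 18k = 18 to 72 of 20 × 26 = 520 planned trials, and 10k = 10 to 40 of 200 practice trials, would lack a written hand rule. For people without paresis these trials are still performed. They lack a written label, not data.

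**3. What the label changes in each analysis.** Let A and B be a participant's two hands, and let d be post-test minus pre-test error.

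- *Group by test, averaged over limb:* each participant contributes (d_A + d_B)/2. Swapping the labels leaves this unchanged.
- *Practice model:* limb is not a term.
- *Limb by test, and group by test by limb:* each participant contributes d_paretic − d_non-paretic. The hand called paretic is always the one that practised, so this is also the practised-versus-unpractised contrast. It is defined for a person with two unaffected hands once one is chosen, and nothing forces it to zero.
- *Limb main effect:* if a share p has no between-limb difference, the average difference D becomes (1 − p)D. For an assumed p of 10% to 30%, that is 0.90D to 0.70D. This is the only term for which the dilution follows directly.

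**4. The one-handed participant.** The inclusion rule and the motor exclusion apply together, and the stricter one decides. The tasks include testing and practice with the paretic hand, so a person who cannot use that hand cannot perform them and falls under the exclusion on its ordinary reading. The pre-test and baseline transfer trials use each hand and come before practice, so an inability that was missed at screening would show there.

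**The case for a change.** The strongest case for acting is that an unwritten choice fixes both the trained hand and a model factor, and one sentence before randomisation would settle it. The registry is not described as a population with arm weakness, and the exclusion names neither a hand nor a check. It can also be argued that the loss of power is material. If 10% to 30% of participants show no limb difference, an effect that had 80% power falls to about 71% to 50%, and restoring it would take 20/(1 − p)², or about 25 to 41 participants.

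The textual part stands: no rule is written, and the two hand criteria fit together awkwardly.

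The power argument does not carry the weight put on it. The 10% to 30% has no source in the documents. By step 3 the figures apply to the limb main effect, and reach the interactions only under the further assumption that practice has no hand-specific effect in these people. A sentence naming the hand would not recover that power anyway, since the same people would remain in the sample. Only excluding them would.

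A second calculation treats 10% to 30% per group as wholly lost, which raises the detectable group difference from 1.25 to between 1.32 and 1.50 SD (normal approximation, two-sided 0.05, 80% power). That overstates the case. Those who cannot use the hand should be screened out, anyone admitted would still contribute non-paretic test trials to the mixed models, and the plan states neither that error rate nor that power.

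**Conclusion.** No change to the plan is needed. What remains is a missing definition that those running the study would fill in the obvious way, by treating the more-affected hand as paretic and recording the choice. That also handles two affected arms. Where the hands truly do not differ, either choice serves, and limb then simply marks which hand practised.

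The randomised comparison of change between groups is not biased, provided the side is chosen on clinical grounds and not according to group. The possible cost is dilution of the limb main effect in proportion to an unknown share of participants, each being 1/20 = 5% of the sample. That effect describes the difference between limbs and does not compare the groups.

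Requiring an identifiable paretic arm would remove even that cost, at the price of a smaller eligible pool and less relevance to people with little arm involvement. In a study of 20, leaving eligibility broad is a fair trade-off. The conclusion assumes that the motor exclusion is applied to the tasks as described, each hand included.

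### Transfer-task conclusions should rest on group × test condition, kept out of stepwise removal, because the pre-post change mixes transfer with retest learning

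*Combined protocol and SAP*

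**What the plan says.** The Transfer Task section gives the motive: therapists expect training on some tasks to help with similar tasks that were not trained. The force task is therefore done before practice "to obtain a baseline level of performance for comparison after practice", and again afterwards. On each occasion the display is live: "Participants will receive visual feedback regarding their level of light touch force production on a visual display". The Design section gives the amount: "Participants will complete 4 trials (2 trials per limb) of the transfer task before and after practice".

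Under Practice, all participants do the laser task: "participants will engage in 10, 1 min practice blocks", with the paretic hand. The randomised difference is physical support during those blocks. The experimental group receives it, and "The control group will receive no physical support to maintain balance". Allocation is described under Participants: "Participants will be randomly assigned to a group", with "10 participants in experimental group, 10 participants in control group".

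The Statistical Analysis section sets the model: "For the transfer task (error score and postural sway metrics), group (experimental, control), test condition (pre-test, immediate post-test), limb (paretic, non-paretic") and their interactions are fixed effects, and participant is a random effect. Model building is backward stepwise, with no retention rule given. Simple effects and pairwise comparisons follow significant interactions. No term is named as the one that carries the transfer conclusion.

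**The concern.** The question that the Transfer Task section raises is whether laser practice helps an untrained task. Answering it from a before-and-after comparison would need someone who repeats the force task without laser practice, and no participant does. The baseline trials are themselves practice on the force task, with a bar, a colour change and a target line showing the error as it occurs. Improvement at post-test may come from that exposure, from the laser practice, or from both.

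The randomised comparison does not have this problem, but the plan neither gives it priority nor protects it. If stepwise selection removes group × test condition, the visible result for the transfer task is a pre-post main effect that has no clear interpretation. What is at stake is the wording of the conclusion: a statement that practice transferred would have no support from the design, while the question the trial can answer might be left without a reported estimate.

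**Working it through.** **Inputs from the documents.** 20 participants, 10 per group (Participants); 30 s force trials with feedback (Transfer Task); 2 trials per limb before and after practice (Design); 10 one-minute laser blocks for everyone (Practice). The plan states no alpha, SD, effect size or power, so all of those below are assumptions.

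**1. The plan's own count.** 2 trials × 2 limbs × 2 test conditions = 8 transfer trials, which agrees with the Design section. Force-task exposure before the post-test is 4 × 30 s = 120 s, or 60 s per limb. Laser practice is 10 × 60 s = 600 s.

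**2. What each term estimates.** Let R be retest learning on the force task, and let Tc and Te be transfer in the control and experimental groups.
- Control gain = R + Tc. Experimental gain = R + Te.
- Test-condition main effect = R + (Tc + Te)/2. R cannot be separated from the rest.
- Group × test condition = (R + Tc) − (R + Te) = Tc − Te. R cancels if it is the same in both groups.
- Limb × test condition = (R paretic − R non-paretic) + (T paretic − T non-paretic). Only the paretic hand practises the laser task, so this carries some information. However, limb is not randomised, the hands may differ in retest gain, and learning may pass between hands.

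**3. Behaviour with no transfer at all (Tc = Te = 0).** Take one change score per participant with SD 1, 10 per group, two-sided 5%, 18 df, critical t = 2.101. The main effect has noncentrality R√20.

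| R (SD of change) | Main effect significant |
|---|---|
| 0 | 5% |
| 0.25 | 19% |
| 0.5 | 56% |
| 0.8 | 92% |
| 1 | 99% |

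A simulation with 20,000 runs per setting gave the same figures, and the group × test contrast was significant in 4.7 to 5.2% of runs at every R. With Tc = 0.5 and Te = 0 the contrast averaged 0.50 at every R.

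**4. Precision of the protected contrast.** Noncentrality = d√(10/2) = 2.236d.
- Power: 19% at d = 0.5, 40% at 0.8, 56% at 1. The difference detectable with 80% power is about 1.32 SD.
- 95% confidence half-width: 2.101 × √(2/10) = 0.94 SD.
- If stepwise selection kept terms at the 5% level (an assumption) and no higher-order term held this one in, it would be removed with probability 1 − power: 81%, 60% and 44%.

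**5. An illustration on the error scale.** Assume force error falls with each exposure k of a hand as k^(−b). Then gain = 1 − mean(3^−b, 4^−b)/mean(1, 2^−b). For b = 0.2: 1 − 0.780/0.935 = 17%. For b = 0.1, 0.2, 0.3, 0.4 the gains are 9, 17, 24 and 31%, with no transfer.

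The SD of a participant's log change is √(2s²/4 + sc²), with trial log SD s and change SD sc:
- s = 0.3, sc = 0.15: √(0.045 + 0.0225) = 0.260.
- s = 0.5, sc = 0.3: √(0.125 + 0.09) = 0.464.

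For b = 0.2 the log shift is −ln(0.834) = 0.181, and noncentrality is 0.181 × √20/0.260 = 3.12 or 0.181 × √20/0.464 = 1.75. With 19 df, the chance of a significant test-condition effect over the four values of b is 31, 84, 99 and 100% in the first case, and 13, 38, 71 and 92% in the second.

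**The case against.** The strongest reply is that the trial's question is the effect of support, as the study title and the description of Experiment 1 show, and that group × test condition answers it without bias from retest learning. A reader might infer from the Transfer Task section that transfer is judged only against each participant's own baseline, so that the whole transfer assessment fails. The documents do not support that: any controlled pre-post design takes a baseline, and the Statistical Analysis section compares changes between randomised groups.

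A reader might also infer that a pre-post gain will be reported as transfer. No section says so. Simple effects are planned only after significant interactions, so within-group changes are not a free-standing route to such a claim. Limb × test condition gives a partial internal comparator. The sizes above depend wholly on assumed learning rates and SDs: they show that retest learning would be detected if present, not that it is present.

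All of this stands. What it leaves untouched is that the Transfer Task section presents the pre-post comparison as the way to assess transfer, that the analysis section does not say which term carries the conclusion, and that stepwise selection can remove the one term that is protected.

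**Conclusion.** The randomised comparison is sound and no planned calculation is wrong. The gap is in what may be concluded. The test-condition main effect and within-group changes on the force task estimate transfer and retest learning together, and limb × test condition separates them only in part. Group × test condition isolates the effect of support, provided that retest learning is the same with and without support. A null result on it would not show that transfer is absent, since equal transfer in both groups also gives zero.

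The point matters in practice because that contrast is weak at 10 per group (about 19% power at 0.5 SD, 40% at 0.8 SD), so data-driven removal is a real prospect, whereas the confounded main effect is comparatively easy to detect (56% at a retest gain of 0.5 SD). Those percentages are illustrations. The identification argument does not depend on them.

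**What to change.** In the Statistical Analysis section:
- Name group × test condition as the contrast on which transfer-task conclusions rest.
- Keep it and its lower-order terms in the model whatever stepwise selection indicates.
- Report its estimate with a confidence interval, whether or not it is significant.
- Label the test-condition main effect and within-group pre-post changes on the force task as *practice plus retest*, not as transfer.

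This costs a few sentences and needs no extra participants, visits or data. The downside is that the general claim that laser practice transfers to the force task is given up.

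An unscored familiarisation trial per hand before the baseline is not a substitute. Under the power-law illustration it moves the scored exposures to 2–3 and 4–5. The retest gain at b = 0.2 then falls only from 17% to 11%, and about 68 to 70% of the gain remains across the four values of b.

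### Transfer-task sway is analysed without the recorded finger force, so sway lowered by pressing above 1 N cannot be told apart from sway lowered by postural control

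*Combined protocol and SAP*

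**What the plan says.** The Transfer Task section asks participants to "produce a specified level of light touch force (0.5-1 N to prevent physical stabilization) on the force transducer". Feedback is a bar on a screen: "The bar will increase in vertical size with increased force production and decrease in size with less force production". Colour marks success or failure, and "When the bar is red, the participant needs to alter the level of force production". A line also marks the target. No rule for stopping, repeating or rejecting a trial is given.

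Under Materials and Apparatus, "light finger force production will be measured with a 1500 g force transducer", and "Postural sway data and light force production will be sampled continuously at a rate of 150 Hz".

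Under Supra-Postural Task Performance, the accuracy measure is "Root mean square (RMS) deviation of the observed supra-postural task performance from the expected values", and "For the transfer task, this will be defined as the deviation from the target range of light touch force production".

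Under Statistical Analysis, the transfer model is set out as follows: "For the transfer task (error score and postural sway metrics), group (experimental, control), test condition (pre-test, immediate post-test), limb (paretic, non-paretic"). The interactions are also fixed effects, and participant is the random effect. No force variable appears in the sway models. The only conditioning of the sway data, given at the start of Proposed Data Analysis, is a 6 Hz low-pass filter.

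**The concern.** The plan gives its own reason for the force window: it keeps the finger from propping up the body. The upper limit therefore does more than define success on the task. It is the condition under which transfer sway can be read as unaided posture. The section on the immediate post-test, which includes the transfer task, likewise says that participants are not supported there.

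Nothing described enforces that condition, and nothing in the analysis checks it. The error score drops the direction of the deviation, and the sway models do not use force. If one group came to press harder after practice, its transfer sway could fall because the sensor was carrying some load. The planned output would not separate that from better postural control. At stake is what a group difference in transfer sway can be taken to mean.

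**Working it through.** The plan gives no figure on this point to reproduce, so the check applies its definitions to simple force profiles. The profiles are illustrative assumptions, not data.

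**Inputs.** Window 0.5 to 1 N (Transfer Task); sensor capacity 1500 g and sampling at 150 Hz (Materials and Apparatus); 30 s trials (Transfer Task); RMS deviation from the range (Supra-Postural Task Performance); 20 participants (Participants) and 8 transfer trials each (Design).

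**Step 1. Can force exceed the limit and be recorded?** 1.5 kg × 9.80665 m/s² = 14.7 N, which is 14.7 times the 1 N limit. The sensor does not cap the force. This is capacity, not evidence that anyone over-presses.

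**Step 2. Error formula.** For each sample with force F: d = F − 1 if F > 1; d = F − 0.5 if F < 0.5; d = 0 otherwise. RMS = √(mean of d²) over 150 × 30 = 4,500 samples. Force is taken as non-negative.

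**Step 3. What RMS can and cannot show.**

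| Profile over 30 s | RMS (N) | Signed mean d (N) | Samples above 1 N |
|---|---|---|---|
| Constant 0.25 N | 0.25 | −0.25 | 0% |
| Constant 1.25 N | 0.25 | +0.25 | 100% |
| No contact, 0 N | 0.50 | −0.50 | 0% |
| Constant 1.5 N | 0.50 | +0.50 | 100% |
| 2 N for 7.5 s, otherwise in range | √(0.25 × 1²) = 0.50 | 0.25 × 1 = +0.25 | 25% |
| Constant 2 N | 1.00 | +1.00 | 100% |
| Constant 3 N | 2.00 | +2.00 | 100% |

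Under-force error cannot exceed 0.5 N, because force cannot fall below zero. Over-force error can reach 14.7 − 1 = 13.7 N. So an RMS up to 0.5 N is ambiguous, and a larger RMS must include some over-force.

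**Step 4. Why two summaries.** Half a trial at 1.25 N and half at 0.25 N gives a signed mean of 0.5 × 0.25 − 0.5 × 0.25 = 0, with RMS 0.25 N and 50% of samples above 1 N. The signed mean alone can cancel; the percentage does not.

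**Step 5. Which sway outcomes are involved.** %DET, MAXLINE, MEANLINE, SampEn and SD of COP, each in two planes, make 10; COP path length makes 11. Only path length is linked to stability in the Traditional Analyses section, where a longer path is commonly read as less stable. SD is described as variability. The other 4 × 2 = 8 measure regularity or predictability.

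**Step 6. What bias requires.** The transfer model has a pre-test baseline and a group-by-test interaction. Over-pressing that is stable from pre-test to post-test largely drops out of that contrast. Bias in the contrast needs over-pressing that changes differently in the two groups.

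**The case against.** The strongest reply is that real leaning is not hidden. A steady 3 N scores 2.0 N, which under-pressing cannot produce, and the error score is itself a transfer outcome. The live bar and colour show over-force at once, and random assignment with a pre-test baseline removes stable habits. All of this stands, and it limits the point. It does not remove it: the ambiguous zone still includes a constant force 50% above the limit, error and sway go into separate models, and no rule says to read them together.

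It can also be said that the plan is silent rather than wrong. That is true: no sentence says that sway will be analysed whatever the force. But silence leaves the handling to be chosen after the data are seen.

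Several stronger readings are tempting and are not supported:

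- A reader might infer that the trial tests whether supported practice makes people dependent on support. The documents speak of learning, transfer, and the regularity of sway.
- A reader might infer that all 11 sway outcomes would be pushed towards looking better. Only path length carries a stated reading in terms of stability.
- A reader might infer that the paretic hand is most at risk, or that pressing too lightly and too hard move sway in opposite directions. The documents address neither.

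**Conclusion.** The point holds as a gap in interpretation. By the plan's own premise, lower sway in the transfer task has two possible explanations, and the specified analysis cannot separate them although the force needed to do so is recorded. The error score is blind to direction up to 0.5 N; above that it reveals over-force, but the sway models do not use it.

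The size of any bias cannot be computed. The documents do not give the share of time above 1 N, its effect on sway, or any difference between groups. If time above 1 N is near zero, or changes equally in both groups, the group-by-test contrast is essentially untouched. A reader might infer that the transfer result is biased or will point the wrong way; the documents do not show that. The conclusion assumes that force above 1 N can stabilise posture, which is the protocol's own rationale. It concerns transfer-task sway only, most clearly COP path length. The laser task is unaffected. This is a low-cost improvement worth making, not a defect that undermines the trial.

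**What to change.** Under Supra-Postural Task Performance, define two further summaries for each transfer trial: the signed mean deviation from the 0.5 to 1 N range, and the percentage of samples above 1 N. Report both by group, hand and test condition.

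Under Statistical Analysis, fit both with the same group × test condition × limb mixed model. Report the group-by-test estimate with its interval even if backward selection would drop it, since that is the estimate to set beside the sway result.

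State the reading rule in advance. If the group with the larger pre-to-post fall in COP path length or SD is also estimated to have the larger rise in time above 1 N, do not attribute the lower sway to postural control alone.

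A sway model adjusted for over-pressing should be left out or labelled exploratory. Over-pressing is measured after randomisation and may itself result from the practice condition, so adjustment could remove part of the effect under study.

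The cost is two more outcomes computed from existing recordings, over 20 × 8 = 160 planned transfer trials, and possibly a more cautious conclusion on transfer sway. The percentage may pile up at zero, so its distribution should be shown as well as the model estimate. No new data collection is needed.
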